### **6.5 Half Yearly Follow Up**

The subjects will be followed every 6 months following surgery for a total of 2 years. At the time of the first 6 month follow up the subjects receiving metformin will return any unused study drug and drug reconciliation will occur.

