## 2 Study Objectives

Primary objective for pilot study:

1. To evaluate the feasibility of patient randomization, accrual, and tissue collection in a pilot study of metformin versus observation following resection of stage IA-IIIA lung squamous cell cancer for patients.
2. To compare the 2-year recurrence free survival (RFS) rate between metformin and observation.

[figure not shown]
Secondary objective(s) for pilot study:

1. To develop the metformin sensitivity index based on iPS cell lines from the first 20 patients randomized to the metformin arm.
2. To apply the metformin sensitivity index on the remaining 25 patients randomized to metformin and the 45 observation patients (70patients total) to compare the 2-year RFS rate between metformin-sensitive and metformin-not-sensitive patients
3. To compare adverse events between metformin and observation arms using CTCAE version 4.

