## 3 Study Design

### 3.1 General Design

Patients will be identified and enrolled from Thoracic Surgical Clinics. Patients will undergo surgical resection with the collection of tumor tissue, normal lung tissue, blood, and skin biopsies. For patients enrolled in the study that were found to have stage IA-IIIA SCC, starting less than 90 days from the time of surgery, patients will be randomized to receive either 850 mg po BID of metformin or observation. Metformin dosing will include a 4 week ramp up of 850 mg po daily prior to starting the BID dose, for a total of 6 months of Metformin. Patients will be followed for 2 years from the time of surgery to evaluate 2-year RFS. We plan to randomize a total of 100 patients (50 per arm), such that 90 patients are evaluable for the primary endpoint.

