### **6.4 Monthly Telephone Calls**

The study team will contact the subjects in the group taking Metformin monthly via telephone to assess drug compliance, adverse events, and any new diagnosis.

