## 7 Statistical Plan

### 7.1 Statistical Methods

All patients meeting the eligibility criteria, and who started treatment, will be considered evaluable for the 2 year RFS rate endpoint. The proportion of 2 year RFS rates (along with the 95% confidence interval) will be estimated within each arm by the number of patients who are recurrence-free and alive at 2 years divided by the total number of evaluable patients in each arm, and compared using a chi-squared test.

Clinical data regarding recurrence-free survival (RFS) will be utilized for development of the metformin sensitivity index. Data collected will be summarized using descriptive statistics, including mean and standard deviation and median and inter quartile range for continuous variables, and using frequencies and percentages for categorical variables. Logistic regression models will be used to assess the impact of metformin sensitivity index metrics, treatment, and the interaction between the metformin sensitivity index metrics and treatment on the 2 year RFS status as the outcome of interest.

Adverse events (AEs) will be compared between metformin and placebo using CTCAE version 4. To evaluate the AE profiles associated with each intervention arm, the maximum grade for each type of AE will be recorded for each participant and frequency tables will be reviewed to determine the overall patterns. The number and severity of AEs (overall and by intervention group) will be tabulated and summarized across all grades. Chi-square tests will be used to compare the AE rates between metformin and placebo.

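### No listed contact records a check for recurrence, and section 7.1 has no category for unverified status, so a living patient not assessed near month 24 can be scored either way

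*Combined protocol and SAP*

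**What the plan says.** Section 2 lists the two-year comparison under the primary objective: "To compare the 2-year recurrence free survival (RFS) rate between metformin and observation". The design in section 3.1 is open: "patients will be randomized to receive either 850 mg po BID of metformin or observation". The same section gives follow-up its purpose, "Patients will be followed for 2 years from the time of surgery to evaluate 2-year RFS", and its size: "We plan to randomize a total of 100 patients (50 per arm), such that 90 patients are evaluable for the primary endpoint".

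The contacts are set out in section 6. Visits 1 to 3 cover consent and a blood sample, surgery with tissue collection, and eligibility with randomisation. Section 6.4 adds monthly telephone calls, for the group taking metformin only, "to assess drug compliance, adverse events, and any new diagnosis". Section 6.5 covers the rest: "The subjects will be followed every 6 months following surgery for a total of 2 years". The one task it names is for the metformin arm: "At the time of the first 6 month follow up the subjects receiving metformin will return any unused study drug and drug reconciliation will occur".

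Section 7.1 treats every eligible patient who started treatment as evaluable. It estimates the rate in each arm as "the number of patients who are recurrence-free and alive at 2 years" over that total, and compares the arms with a chi-squared test.

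**The concern.** The endpoint needs a known recurrence status for every living patient at two years, and the plan does not say how that status is obtained. There is no definition of recurrence, no examination or imaging item, no window around month 24 and no stated recurrence data field. The estimator has two states and a fixed denominator, so a patient whose status was never verified must still be placed in one of them.

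Two problems follow. First, the rate depends on an unwritten coding choice. Counting unverified patients as successes overstates RFS if any have recurred. Counting them as failures understates it if any have not. Second, arm is known to patient and study team, and the only listed question about new diagnoses goes to one arm. If recurrence is looked for more in one arm, the difference between arms is biased.

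The same two-year status is the outcome in the sensitivity-index regression models of section 7.1 and in the second secondary objective, so misclassification carries over to both.

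**Working it through.** **Inputs from the documents.** 100 randomised, 50 per arm, 90 evaluable (section 3.1). The secondary objectives split the 90 as 20 + 25 = 45 metformin and 45 observation. Background recurrence of 30-70% by stage (section 1.1), not stated to be a two-year figure and used here only as a range.

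**Assumed inputs.** Detection rates, a two-sided 5% test without continuity correction, and every RFS event a recurrence. The documents give none of these.

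**The plan's own figure.** 90 / (1 - 0.10) = 100, so 100 randomised for 90 evaluable is reproduced with 10% loss. That 10% is implied, not stated. No significance level, power or effect size is given, so the 90 itself cannot be derived.

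**Effect of the coding choice.** One patient of unverified status moves an arm's rate by 1/45 = 2.2 points. Five move it by 5/45 = 11.1 points, and nine by 9/45 = 20 points. For scale, a significant chi-squared result at 45 per arm needs a difference of about 8 to 10 patients (18 to 22 points).

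**Effect of unequal detection.** Observed RFS = 1 - recurrence x detection. With the same true recurrence in both arms, the spurious difference is recurrence x (gap in detection).

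| True recurrence | Metformin, 95% detected | Observation, 90% detected | Observation, 85% detected | Spurious difference |
|---|---|---|---|---|
| 30% | 71.5% | 73.0% | 74.5% | 1.5 to 3 points |
| 40% | 62.0% | 64.0% | 66.0% | 2 to 4 points |
| 50% | 52.5% | 55.0% | 57.5% | 2.5 to 5 points |

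The sign reverses if the observation arm is examined more.

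**Effect on the test.** The exact rejection probability at 45 per arm with no true difference is 5.1% to 7.0% over this table. With full detection in both arms it is 4.5% to 5.3%. A larger assumed gap of 100% v 80% gives 10%, 15% and 28% at 30%, 50% and 70% recurrence. Nothing in the documents suggests a gap of that size.

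**The case against.** Several points on the other side stand.

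- A reader might infer that the plan scores an unchecked living patient as recurrence-free. Section 7.1 contains no such rule. Read strictly, a patient of unknown status is not known to be recurrence-free and could be left out of the numerator. What the text supports is that no rule exists.
- A reader might take section 6.5 to mean that follow-up is for drug return only. The study summary and section 3.1 say that both arms are followed in order to evaluate RFS, so the purpose is stated and only the procedure is missing.
- Section 8.2 requires adverse-event questioning at each contact, and section 9.3 requires missing CRF data to be explained. These help only in part. Section 8.1 generally keeps hospitalisation for treatment of the target disease out of adverse-event reporting. Section 9.3 applies only to what the CRF requests, and the CRF is not in the documents.
- The monthly calls are the one written asymmetry between the arms. If they stop with metformin at six months, their effect on status at two years may be small.
- The detection rates are invented for illustration, and deaths count as failures whether or not recurrence was found. A bias of 2 to 4 points is about one or two patients of 45. It is small beside a 95% confidence half-width of about 20 points for the difference.

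That this is a pilot does not answer the point. The introduction says its data are to help judge whether a phase III trial is feasible and justified, and equal ascertainment of recurrence is part of that.

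**Conclusion.** The concern holds as a gap in ascertainment joined to an estimator that cannot represent unverified status. The firm figure is 2.2 points per unverified living patient and about 11 points for five, given 45 evaluable per arm. How many such patients there will be cannot be known from the documents.

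Bias from unequal, unblinded detection is possible in either direction. The range of 1.5 to 5 points rests wholly on assumed detection and recurrence rates. The documents do not support the stronger inference that the comparison is tilted against metformin, or that the false-positive rate is materially raised. The first would need evidence that metformin patients are examined more through to month 24, and the second a much larger detection gap. The change is worth making because it is cheap and removes an arbitrary coding choice from a primary-objective comparison.

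**What to change.** 1. **Section 6.5.** At every half-yearly contact in both arms, record recurrence status, its date, its basis (biopsy, imaging or clinical) and the date of the latest chest imaging done in routine care. Ask the same question about new diagnoses in both arms.
2. **Section 7.1.** Count a patient as recurrence-free at two years only if an assessment is documented in a stated window around month 24. Estimate two-year RFS by Kaplan-Meier, with recurrences and deaths as events and patients of unverified status censored at their last documented assessment. Compare the arms at 24 months. This assumes that being unverified is unrelated to recurrence risk, which should be stated. If the simple proportion is kept, report the number unknown by arm, with bounds counting them all as successes and all as failures, because a proportion cannot hold a censored patient.
3. **Reporting.** Tabulate assessment dates by arm. Abstracting routine-care results does not remove unequal looking, but it makes it visible.

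No added scans or readers are needed. The cost is one CRF page filled from existing records, a rewritten estimator paragraph in 7.1, and somewhat wider intervals because some patients will not be assessed at two years.

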## Study Summary

Title	A pilot study of metformin as a chemoprevention agent in non-small cell lung cancer
Running Title	A pilot study of metformin as a chemoprevention agent in non-small cell lung cancer
Protocol Number	12-006865
Phase	Phase II-Pilot study
Methodology	Patients will be identified and enrolled from Thoracic Surgical Clinics. Patients will undergo surgical resection with the collection of tumor tissue, normal lung, blood, and skin biopsies. For patients enrolled in the study that were found to have stage IA-IIIA SCC, starting less than 90 days from the time of surgery, patients will be randomized to receive either 850 mg po BID of metformin or observation. Metformin dosing will include a 4 week ramp up of 850 mg po daily prior to starting the BID dose, for a total of 6 months of Metformin. Patients will be followed for 2 years from the time of surgery to evaluate 2-year Recurrence Free Survival.
Overall Study Duration	08/01/2012 to 07/30/2017
Subject Participation Duration	2 Years
Single or Multi-Site	Single Site
Objectives	
 
1. To evaluate the feasibility of patient randomization, accrual, and tissue collection in a pilot study of metformin versus observation following resection of stage IA-IIIA lung squamous cell cancer for patients.
 
2. To compare the 2-year recurrence free survival rate between metformin and observation.
 

Number of Subjects	100
Diagnosis and Main Inclusion Criteria	Suspected or biopsy proven Stage IA-IIIA NSCLC (must be proven squamous cell carcinoma at the time of surgery)medically fit for surgical resection (based on surgeon assessment), current or prior smoker, age >18, no existing untreated or prior cancer <5 years from diagnosis, willing and able to consent to study, undergo study interventions, and take study drug; not diabetic or currently taking metformin or other diabetic drug, ECOG performance status 0,1, or 2.
Study Product, Dose, Route, Regimen	Metformin dosing will include a 4 week ramp up of 850 mg po daily prior to starting the BID dose.
Duration of Administration	Six Months

Reference therapy	Observation
-------------------	-------------

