## 4 Subject Selection Enrollment and Withdrawal

### 4.1 Inclusion Criteria

- Suspected or biopsy proven Stage IA-IIIA lung squamous cell carcinoma (must be proven SCC at the time of surgery)
- Medically fit for surgical resection (based on surgeon assessment)
- Current or prior smoker
- Age > 18 years old
- Both Male and Female
- Willing and able to consent to study, undergo study interventions, and take study drug
- ECOG performance status 0, 1, 2
- Subject must start Metformin within 90 days of surgery.

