### **5.8.3 Return or Destruction of Study Drug**

The remaining study agent will be returned to the study team following 6 months of metformin administration. At the completion of the study, there will be a final reconciliation of drug shipped, drug dispensed, drug returns, and drug remaining. This reconciliation will be logged on the drug reconciliation form, signed and dated. Any discrepancies noted will be documented and investigated, prior to return or destruction of unused study drug. Drug destroyed on site will be documented in the study files.

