### **6.3 Visit 3**

At the time of the subjects follow up (less than 90 days from the time of surgery) the subject will be seen by the study team. Eligibility criteria will be assessed and if the subject is still eligible they will be randomized and receive their study treatment (metformin or observation).

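### Section 6.5 times the return of unused metformin from surgery, although the 6-month course starts later, at Visit 3, and 5.8.3 times return after 6 months of drug

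*Combined protocol and SAP*

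**What the plan says.** Section 6.5 sets its own time origin: "The subjects will be followed every 6 months following surgery for a total of 2 years". Its next sentence ties drug return to the first of those visits: "At the time of the first 6 month follow up the subjects receiving metformin will return any unused study drug". Reconciliation is placed at that same visit.

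Other sections describe a different clock:

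- **Start of drug.** Under 6.3, patients are randomized and receive their assigned treatment at Visit 3, a follow-up less than 90 days after surgery. Section 4.1 adds: "Subject must start Metformin within 90 days of surgery".
- **Length of course.** The Study Summary and 3.1 both specify a 4-week ramp-up at one capsule a day, then twice-daily dosing, "for a total of 6 months of Metformin".
- **Time of return.** Section 5.8.3 says: "The remaining study agent will be returned to the study team following 6 months of metformin administration". It also calls for a final reconciliation when the study is complete, with any discrepancies documented and investigated.
- **Adherence.** Section 5.5 provides a medication diary and monthly calls. Section 6.4 repeats the calls: "The study team will contact the subjects in the group taking Metformin monthly via telephone to assess drug compliance".

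**The concern.** The two return rules use different time origins: surgery in 6.5, first dose in 5.8.3. They give the same date only if metformin starts on the day of surgery, and the Visit 3 schedule does not provide for that. At the 6.5 visit, a patient who is taking the full course therefore still has doses to come.

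Staff at that visit have a written instruction to take back unused drug and no statement that the patient should keep what is still due. There are two possible outcomes:

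- They keep the capsules. The patient then receives less than the specified 6 months, by an amount that varies with the start date.
- They count the capsules and hand them back. The count then describes an unfinished course and cannot serve as the end-of-treatment reconciliation.

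No half-yearly visit is scheduled at the end of the course, so 6.5 as written does not say when the end-of-course return should take place.

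**Working it through.** The plan states no figure for this point, so there is none to reproduce. The check is date and capsule arithmetic.

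**Inputs from the documents**
- Visits at 6, 12, 18 and 24 months after surgery (6.5).
- Start at Visit 3, so day 89 at the latest (6.3); 4.1 allows a start within 90 days.
- Course of 6 months, with 4 weeks at one 850 mg capsule daily and then two daily (3.1, 5.1).

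**Assumptions, because the documents give no visit window and no distribution of start days**
- 6 months = 183 days, and the first half-yearly visit falls on day 183 after surgery.
- Every dose is taken.
- Start days of 14, 30, 60 and 89 are illustrative.

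**Formulas**, with s the start day counted from surgery
- Full course: 28 × 1 + 155 × 2 = 338 capsules.
- Days on drug at the visit: 183 − s.
- Capsules taken by then: 28 + 2 × (183 − s − 28) = 338 − 2s.
- Capsules still due: 338 − (338 − 2s) = 2s.
- Course end: day s + 183.
- Course days left at the visit: (s + 183) − 183 = s, which is the surgery-to-start delay.

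**Results**

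| Start day | Days on drug at visit | Course days left | Capsules taken | Capsules still due | Course ends after surgery |
|---|---|---|---|---|---|
| 14 | 169 | 14 (8%) | 310 | 28 (8%) | day 197 (6.5 months) |
| 30 | 153 | 30 (16%) | 278 | 60 (18%) | day 213 (7.0 months) |
| 60 | 123 | 60 (33%) | 218 | 120 (36%) | day 243 (8.0 months) |
| 89 | 94 | 89 (49%) | 160 | 178 (53%) | day 272 (8.9 months) |

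As a worked line, a day-30 start gives 183 − 30 = 153 days on drug, 28 + 2 × 125 = 278 capsules taken, and 338 − 278 = 60 still due.

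Every course in the table ends after the 6-month visit and before the 12-month visit. Return under 5.8.3 can therefore always take place by the 12-month visit.

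An interim count also needs the right denominator. Judged against the full 338, a fully adherent day-30 starter would show 278/338 = 82% and a day-60 starter 218/338 = 64%. Both are below the 90% level at which 5.5 calls for counselling. Section 5.5 relies on the diary and calls and does not say that capsule counts are used this way, so this is a caution and not a predicted error.

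**The case against.** The strongest reply is that 6.5 and 5.8.3 can be reconciled. Section 5.8.3 sets an earliest time and does not fix a single occasion. Section 6.5 does not call its return final. Drug is supplied in 3-month increments (5.7). An interim return and count at 6 months, followed by return of the remainder after the course, arguably satisfies both. This stands in part: a reader might infer that the two sections can never both be followed, and the documents do not support going that far. The interim reading has to be supplied by the reader, however. The plain instruction in 6.5 is to return unused drug, and its preceding sentence fixes the visit to surgery.

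Second, loss of exposure requires staff to take capsules from a patient in mid-course, against the 6-month course in the Study Summary, 3.1 and 5.8.3. The diary and monthly calls make an unnoticed stop less likely. This also stands, and it makes the harm conditional. A reader might infer that the protocol tells patients to stop at 6 months after surgery; no section says so.

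Third, 5.8.3 provides a final reconciliation at study completion, so an incomplete count under 6.5 would not be the last word on drug accountability. That largely answers the risk from handing drug back. It does not restore doses that a patient was prevented from taking.

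Fourth, the statistical consequence is limited. Section 7.1 compares 2-year recurrence-free survival proportions and uses no capsule counts. A reader might infer that the primary comparison is compromised; nothing in the documents shows that.

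**Conclusion.** The point holds as an operational inconsistency that should be corrected. Section 6.5 followed literally collects drug from patients who are still on course, and it would shorten their exposure by the surgery-to-start delay if the drug were kept.

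Under the assumptions shown, the shortfall is 30 days or 60 of 338 capsules for a day-30 start, and at most about 89 days or 178 capsules for a day-89 start. It is small for early starters. The reading that about half the course is lost applies only near the 90-day limit; the documents give no start-day distribution that would make it typical. These figures measure the course remaining at the visit, not exposure shown to be lost.

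The sample size, the error rates and the 7.1 analyses are not directly affected. Confidence is high on the mismatch in timing. Whether harm follows depends on how staff act at the visit.

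**What to change.** Amend 6.5 in one or two sentences, to this effect:

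- Metformin continues for 6 months from each patient's first dose. Unused drug is returned and reconciled after that course is complete, in line with 5.8.3, at the next contact or visit and no later than the 12-month visit.
- Any capsule count at the 6-month post-surgery visit is interim and is judged against the doses due since the patient's actual start date. The patient keeps the drug.

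Return by mail is an option for sites wanting an earlier reconciliation. The pharmacy already mails refills outward (5.4), but a return mailing would be new, and the correction does not depend on it.

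The cost is a short text change, with no added visit and no change to the analysis. The downside is that return and reconciliation come a few months later for some patients: at the 12-month visit, the latest point allowed, they fall 6 months after the date 6.5 now sets. The final reconciliation in 5.8.3 stays as it is.
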